5.6. Other Considerations for Data Analyses and Data Handling Conventions

Other considerations for data analyses and data handling conventions are outlined in the appendices:

Section	Component
15.3	Appendix 3: Assessment Windows
15.4	Appendix 4: Study Phases and Treatment Emergent Adverse Events

Section	Component
15.5	Appendix 5: Data Display Standards & Handling Conventions
15.6	Appendix 6: Derived and Transformed Data
15.7	Appendix 7: Reporting Standards for Missing Data
15.8	Appendix 8: Values of Potential Clinical Importance
15.9	Appendix 9: Snapshot Algorithm Details
15.10	Appendix 10: Variables Defined for Time to Event Analysis
15.11	Appendix 11: Identification of Adverse Events of Special Interest
15.12	Appendix 12: IDMC

6. STUDY POPULATION ANALYSES

6.1. Overview of Planned Study Population Analyses

The study population analyses will be based on the Intent-to-Treat Exposed population, unless otherwise specified.

Study population analyses including analyses of subject's disposition, protocol deviations, demographic and baseline characteristics, prior and concomitant medications, and oral study treatment accountability will be based on GSK Core Data Standards.

[Table 1](#) provides an overview of the planned study population analyses, with details of the planned displays are presented in [Appendix 14: List of Data Displays](#).

Table 1 Overview of Planned Study Population Analyses

Display Type	Data Displays Generated	
	Table	Listing
Randomization		
Randomization ^[1]		Y ^[2]
Subject Disposition		
Study Populations ^[3]	Y	
Study Recruitment ^[3]	Y	
Reasons for Screening Failures ^[3]	Y	Y
Rescreened Subjects ^[3]		Y
Age Ranges	Y	
Subject Disposition	Y ^{[4][5]}	
Reasons for Withdrawal	Y ^{[4][5]}	Y
IP Discontinuation	Y	Y
Important Protocol Deviations	Y	Y

Display Type	Data Displays Generated	
	Table	Listing
Deviations leading to exclusion from PP	Y	Y
Inclusion and Exclusion Criteria Deviations	Y	Y
Demography and Baseline		
Demographics Characteristics ^[6]	Y	Y
Race & Racial Combinations ^[7]	Y	Y
Hepatitis Status at Entry	Y	
Baseline CDC Classification of HIV infection (2014)	Y	
Baseline Cardiovascular Risk Assessments	Y	
Distribution of CD4+ Cell Counts at Screening and Baseline	Y	
Prior Exposure to CAB+RPV	Y	
HIV-1 Risk Factors	Y	
Medical Conditions, Concomitant Medications & Antiretroviral Therapy		
Medical Conditions (Current/Past) ^[8]	Y	
Medical Conditions: Sub-conditions (Current/Past) ^[9, 10]	Y	
Concomitant Medications (non-ART)	Y ^[10]	
Prior ART Medications	Y	Y
Concomitant ART Medications during Maintenance Phase		Y
ART Medications Received during LTFU Phase		Y
Lipid Modifying Agents (Baseline and during Maintenance Phase)	Y	
Substance use at Entry	Y	
Medical History of Seizure		Y
Other		
Oral Study Treatment Accountability ^[11]		Y

NOTES:

- T = Tables, L = Listings, Y = Display Generated,
- 1. Base on Randomized population.
- 2. One listing of participants randomized but not treated, and one listing of randomized and actual strata and treatment assignment.
- 3. All Subjects screened population.
- 4. Participants who have not been recorded as either completing or withdrawing from the study will be categorized as "Ongoing at time of the analysis" for summary purposes.
- 5. Analysis of subject disposition will be performed for each Study Phase separately, as well as for overall study conclusion.
- 6. Age and ethnicity collected at Screening; weight and height collected at Baseline.
- 7. The five high level FDA race categories and designated Asian subcategories will be summarised along with all combinations of high level categories which exist in the data. The nine race categories collected will be summarised along with categories for mixed race. A by-subject listing of race will also be produced.
- 8. Medical conditions will be coded using the Medical Dictionary for Regulatory Activities (MedDRA).
- 9. Sub conditions are Cardiac, Gastrointestinal, Metabolism and Nutrition, Psychiatric, Renal and Urinary, and Nervous System Conditions.
- 10. summarised by, Ingredient combinations.
- 11. Dispensation information (dates and number of tablets dispensed and returned).

6.2. Prior and Concomitant Medications

Non-ART and/or ART Medications will be classified by categories shown in [Table 2](#). The same medication may be classified by more than one categories. For example, if the Non-ART medication was started after the maintenance treatment start date and was stopped at nominal Week 104 visit while subject was still receiving study treatment, this medication would be considered both ‘concomitant during maintenance’ and ‘concomitant during extension’.

Table 2 Derived Data for Non-ART Medications/ART Medications

	Definition
Prior	ART Medication Taken \leq Maintenance Treatment Start Date Non-ART Medication Taken $<$ Maintenance Treatment Start Date
Concomitant during Maintenance	For subjects continuing into Extension Phase: Maintenance Treatment Start Date \leq Non-ART Medication Taken $<$ Date of Nominal Week 100 Visit Maintenance Treatment Start Date $<$ ART Medication Taken \leq Date of Nominal Week 100 Visit For subjects not continuing into Extension Phase^[a]: Maintenance Treatment Start Date \leq Non-ART Medication Taken $<$ LTFU ART Start Date Maintenance Treatment Start Date $<$ ART Medication Taken $<$ LTFU ART Start Date
Concomitant during Extension	For subjects continuing into Extension Phase^[a]: Date of Nominal Week 100 Visit \leq Non-ART Medication Taken $<$ LTFU ART Start Date Date of Nominal Week 100 Visit $<$ ART Medication Taken $<$ LTFU ART Start Date
Received during Long-term Follow-up	For subjects Who received at least one CAB and/or RPV injection and have started LTFU ART: Non-ART/ART Medication Taken \geq LTFU ART Start Date

NOTES:

- Please refer to [Appendix 7: Reporting Standards for Missing Data](#) for handling of missing and partial dates for medications. Use the rules in this table if medication date is completely missing.
- [a] If subjects have missing LTFU ART start date, only the lower bound will be considered in the derivation.

7. EFFICACY ANALYSES

7.1. Primary Efficacy Analyses

7.1.1. Endpoint / Variables

Proportion of participants with plasma HIV-1 RNA ≥ 50 c/mL as per Food and Drug Administration (FDA) Snapshot algorithm at Week 48 (Intent-to-Treat Exposed [ITT-E] population); see Section 15.9 for additional details.

7.1.2. Summary Measure

Difference in the proportion of participants with HIV-1 RNA ≥ 50 c/mL at Week 48 (defined by the US FDA snapshot algorithm) between each treatment group (Q8W – Q4W).

7.1.3. Population of Interest

The primary efficacy analyses will be based on the Intent-to-Treat Exposed population, unless otherwise specified.

7.1.4. Strategy for Intercurrent (Post-Randomization) Events

As defined by the Snapshot algorithm, HIV-1 RNA ≥ 50 c/mL is determined by the last available HIV-1 RNA measurement while the participant is on treatment within the analysis visit window of interest.

Participants without on-treatment HIV-1 RNA data for the visit of interest and who discontinue treatment for reasons not related to adverse event while having HIV-1 RNA ≥ 50 c/mL at time of discontinuation or who change study treatment not permitted per protocol before the analysis window are classified as having HIV-1 RNA ≥ 50 c/mL.

7.1.5. Statistical Analyses / Methods

Details of the planned displays are provided in [Appendix 14: List of Data Displays](#) and will be based on GSK data standards and statistical principles.

Unless otherwise specified, endpoints / variables defined in Section 7.1.1 will be summarised using descriptive statistics, graphically presented (where appropriate) and listed.

7.1.5.1. Statistical Methodology Specification

Endpoint

 Proportion of Participants with plasma HIV-1 RNA ≥ 50 c/mL at Week 48 using the Snapshot algorithm for the ITT-E population. Subjects with 'HIV-1 RNA ≥ 50 c/mL' per Snapshot algorithm include those who had plasma HIV-1 RNA ≥ 50 c/mL at Week 48, who discontinued for lack of efficacy, who discontinued for other reasons while not < 50 c/mL, or who changed ART.

Snapshot Dataset

- Virologic outcome ('HIV-1 RNA <50 c/mL' or 'HIV-1 RNA ≥ 50 c/mL') per Snapshot algorithm is determined by the last available on-treatment HIV-1 RNA measurement within the analysis visit window of interest (please refer to analysis window defined in [Table 10](#)). In addition, subjects who discontinue for reasons not related to adverse event with on-treatment HIV-1 RNA result at the time of discontinuation ≥ 50 c/mL or who change study treatment not permitted per protocol during maintenance phase before the analysis visit are classified as 'HIV-1 RNA ≥ 50 c/mL'.
- Full details of the Snapshot algorithm are provided in [Section 15.9](#).

Model Specification

- The primary efficacy endpoint will be analysed using a stratified analysis with Cochran-Mantel-Haenszel (CMH) weights, adjusting for the rederived randomization strata corresponding to prior exposure to CAB+RPV (0 weeks, 1-24 weeks, >24 weeks)
- The CMH estimate of the adjusted treatment difference will be calculated as a weighted average of strata-specific estimates of the treatment difference calculated within each stratum as follows:
 - If n_k is the number of Q8W treated participants, m_k is the number of Q4W arm treated participants, and $N_k = n_k + m_k$ is the total number of participants in the k th stratum, then the CMH estimate is given by

$$\hat{d}_{cmh} = \frac{\sum W_k \hat{d}_k}{\sum W_k}$$

where

$$W_k = \frac{n_k m_k}{N_k}$$

are CMH weights and \hat{d}_k are estimates of the differences in proportions between the two treatment arms, $f_{Q8W} - f_{Q4W}$, for the k th stratum.

- The corresponding two-sided 95% CI will be calculated as

$$\hat{d}_{cmh} \pm 1.96 \times \sqrt{\hat{var}(\hat{d}_{cmh})}$$

where the variance estimator [[Sato, 1989](#)] is consistent in both sparse data and large strata and is given below:

$$\hat{var}(\hat{d}_{cmh}) = \frac{\hat{d}_{cmh}(\sum P_k) + \sum Q_k}{(\sum n_k m_k / N_k)^2} = \frac{\hat{d}_{cmh}(\sum P_k) + \sum Q_k}{(\sum W_k)^2}$$

where

$$P_k = \frac{n_k^2 y_k - m_k^2 x_k + n_k m_k (m_k - n_k) / 2}{N_k^2}$$

$$Q_k = \frac{x_k (m_k - y_k) / N_k + y_k (n_k - x_k) / N_k}{2}$$

with x_k and y_k corresponding to the number of participants with Plasma HIV-1 RNA ≥ 50 c/mL at Week 48 per FDA Snapshot for Q8W and Q4W, respectively, for the k th stratum.

Model Results Presentation

- Adjusted CMH estimate of the difference in the proportion of subjects with Plasma HIV-1 ≥ 50 c/mL between each treatment group (Q8W – Q4W) and corresponding 95% confidence interval.
- Non-inferiority will be concluded if the upper bound of the two-sided 95% confidence interval for the CMH adjusted treatment difference (Q8W – Q4W) is less than 4%.
- If this analysis shows non-inferiority, then a superiority hypothesis will be tested at the two-sided 5% level of significance. Superiority favoring Q8W will be declared if the upper bound of the confidence interval is below 0% for the ITT-E population analysis. If superiority is declared, the p-value for superiority will also be calculated.

Subgroup Analyses

1. Treatment Heterogeneity across rederived randomization strata [prior exposure to CAB+RPV (0 weeks, 1-24 weeks, >24 weeks)]:
 - The weighted least squares chi-squared statistic [Fleiss, 1981] will be used to test for one-way homogeneity across the levels of each categorical variable, with each categorical variable considered separately.
 - Following Lui and Kelly [Lui, 2000] $\frac{1}{2}$ will be added to each cell in any strata for which the stratum-specific rate estimates of either f_{Q8W} or f_{Q4W} are zero or one, and tests will be one-sided.
 - Any heterogeneity found to be statistically significant will be explored and if necessary results will be reported for each level of the categorical variable. Investigation of heterogeneity will be confined to the primary endpoint. Tests of homogeneity will be assessed at the one-sided 10% level of significance.
2. Stratum-specific analyses for two groups of participants: (Group 1) those currently receiving Standard of Care antiretroviral therapy at Baseline (i.e. no prior exposure to CAB+RPV), (Group 2) those receiving Q4W CAB LA + RPV LA therapy in the ongoing ATLAS study (i.e. have prior exposure to CAB+RPV). For each stratum (Group 1 and Group 2), the following will be presented:
 - Proportion of subjects with plasma HIV-1 RNA ≥ 50 c/mL at Week 48 by treatment group.
 - Unadjusted difference in proportions between treatment groups and corresponding two-sided 95% CI.
 - Summary of study outcomes (i.e. HIV-1 RNA < 50 c/mL, HIV-1 RNA ≥ 50 c/mL and reason for no data in the window)

For Group 2, a stratum-adjusted analysis will also be provided, with adjustment for prior CAB+RPV

exposure (1 to 24 weeks vs. >24 weeks) using Cochran-Mantel Haenszel (CMH) weights, as described in the model specification above for the overall primary analysis.

3. Exploration of Subgroups

- An analysis for subgroups listed in Section 5.4.2 will be performed. This will show the proportion of subjects with plasma HIV-1 RNA ≥ 50 c/mL at the time of analysis (Week 48) based on the Snapshot algorithm and will be presented by treatment group.
- Unadjusted difference in proportions between treatment groups and corresponding two-sided 95% CI will also be presented by subgroups. The confidence interval will be calculated using an unconditional exact method [Chan et al, 1999] with two inverted one-sided tests based on the score statistic. These results will also be presented graphically.
- Summary of study outcomes (i.e. HIV-1 RNA < 50 c/mL, HIV-1 RNA ≥ 50 c/mL or reason for no data in the window) by subgroup will be produced.

Note: These subgroup analyses will be exploratory and likely underpowered so that interpretation may therefore focus on point estimates as well as the upper bounds of 95% CIs for the treatment differences and response rates. Additionally, multiple comparisons are being made which inflates the risk of false positive findings. Therefore, if consistent findings across the multiple comparisons were observed then these analyses would still be suggestive of a generalizable finding of non-inferiority.

Sensitivity and Supportive Analyses

1. Per-protocol population analysis:

- To assess the impact of important protocol deviations, statistical analysis will be repeated using the Per-protocol population and compared for consistency with the results from the primary ITT-E population analysis.

7.2. Secondary Efficacy Analyses

7.2.1. Endpoints

The key secondary efficacy endpoint is the proportion of participants with plasma HIV-1 RNA < 50 c/mL at Week 48 using the FDA Snapshot algorithm (Intent-to-Treat Exposed [ITT-E] population).

Other secondary efficacy endpoints for the study are listed below:

- Proportion of participants with plasma HIV-1 RNA < 50 c/mL at Week 24 and Week 96 using the FDA Snapshot algorithm (ITT-E population)
- Proportion of participants with protocol-defined confirmed virologic failure (CVF) through Week 24, Week 48 and Week 96
- Proportion of participants with HIV-1 RNA ≥ 50 c/mL as per FDA Snapshot algorithm at Week 24 and Week 96
- Absolute values and changes from Baseline in viral load and CD4+ cell counts over time including Week 48 and Week 96

7.2.2. Summary Measure

Difference in the proportion of participants with HIV-1 RNA < 50 c/mL at Week 48 and Week 96 (defined by the US FDA snapshot algorithm) between each treatment group (Q8W – Q4W).

Difference in the proportion of participants with HIV-1 RNA \geq 50 c/mL at Week 24 and Week 96 (defined by the US FDA snapshot algorithm) between each treatment group (Q8W – Q4W).

7.2.3. Population of Interest

The secondary efficacy analyses will be based on the Intent-to-Treat Exposed population, unless otherwise specified.

7.2.4. Strategy for Intercurrent (Post-Randomization) Events

As defined by the snapshot algorithm, participants with last available HIV-1 RNA measurement less than 50 c/mL while the participant is on treatment within the analysis visit window of interest are classified as HIV-1 RNA < 50 c/mL.

Participants without on-treatment HIV-1 RNA data for the visit of interest and who discontinue treatment for reasons not related to adverse event while having HIV-1 RNA \geq 50 c/mL at time of discontinuation or who change study treatment not permitted per protocol before the analysis window are classified as having HIV-1 RNA \geq 50 c/mL.

7.2.5. Statistical Analyses / Methods

Details of the planned displays are provided in [Appendix 14: List of Data Displays](#) and will be based on GSK data standards and statistical principles.

Unless otherwise specified, endpoints / variables defined in Section [7.2.1](#) will be summarised using descriptive statistics, graphically presented (where appropriate) and listed.

7.2.5.1. Statistical Methodology Specification

Key Secondary Statistical Analysis
Endpoint

 Proportion of participants with plasma HIV-1 RNA <50 c/mL at Week 48 using the FDA Snapshot algorithm (Intent-to-Treat Exposed [ITT-E] population)
Snapshot Dataset

 As Section 7.1.5.1 and Section 15.9
Model Specification

 As specified in Section 7.1.5.1 but with 'HIV-1 RNA <50 c/mL' replacing HIV-1 \geq 50 c/mL
Model Results Presentation

 Adjusted CMH estimate of the difference in the proportion of participants with HIV-1 RNA < 50

Key Secondary Statistical Analysis
c/mL at Week 48 between each treatment group (Q8W – Q4W) and corresponding 95% confidence interval. 
• Non-inferiority will be concluded if the lower bound of the two-sided 95% confidence interval for the CMH adjusted treatment difference (Q8W – Q4W) is greater than -10%.
Subgroup Analyses

• As specified in Section 7.1.5.1 but with HIV-1 RNA < 50 c/mL replacing 'HIV-1 RNA ≥ 50 c/mL.
Sensitivity and Supportive Analyses
1. Per-protocol population analysis: 
• To assess the impact of important protocol deviations, statistical analysis will be repeated using the Per-protocol population and compared for consistency with the results from the primary ITT-E population analysis.

7.3. Exploratory Efficacy Analyses

Table 3 provides an overview of the planned exploratory efficacy analyses. Details of the planned displays are provided in Appendix 14: List of Data Displays and will be based on GSK data standards and statistical principles. The exploratory efficacy analyses will be based on the Intent-to-Treat Exposed population, unless otherwise specified.

Table 3 Overview of Exploratory Efficacy Analyses

Endpoints	Absolute							Change from Baseline						
	Stats Analysis			Summary		Individual		Stats Analysis			Summary		Individual	
	T	F	L	T	F	F	L	T	F	L	T	F	F	L
Proportion of participants without efficacy-related discontinuation (ERDF) or treatment-related discontinuation (TRDF) failure at Week 24/Week 48/Week 96														
Kaplan-Meier estimate				Y										
Proportion of participants with plasma HIV-1 RNA ≥ 50 c/mL over time (Maintenance Phase) - Snapshot														
by visit				Y	Y ^[1]									
By visit and subgroup				Y	Y ^[2]									
Proportion of participants with plasma HIV-1 RNA < 50 c/mL over time (Maintenance Phase) - Snapshot														
by visit				Y	Y ^[3]									
By visit and subgroup				Y	Y ^[2]									
Proportion of participants with plasma HIV-1 RNA ≥ 200 c/mL over time (Maintenance Phase) - Snapshot														
by visit				Y ^[4]	Y ^[5]									
Proportion of participants with plasma HIV-1 RNA < 200 c/mL over time (Maintenance Phase) - Snapshot														
by visit				Y ^[4]	Y ^[5]									
Proportion of participants with plasma HIV-1 RNA ≥ 50 c/mL at Week 48/Week 96 by delay in IP injection - Snapshot														
by delay in IP injection ^[6]				Y										
Proportion of participants with plasma HIV-1 RNA < 2 c/mL over time (Maintenance Phase)														
by visit				Y										
Plasma HIV-1 RNA over time														
by visit				Y ^[7]		Y ^[8]	Y ^[9]							Y ^[9]
Target Detected vs Target Not Detected by visit ^[10]				Y			Y ^[11]							
Confirmed Virologic Failure (CVF)														
CVF overall				Y										
CVF by visit				Y		Y								

Endpoints	Absolute							Change from Baseline						
	Stats Analysis			Summary		Individual		Stats Analysis			Summary		Individual	
	T	F	L	T	F	F	L	T	F	L	T	F	F	L
Plasma HIV-1 RNA at time of suspected and confirmed virologic failure				Y										
CD4+ & CD8+ Cell Counts Over Time														
CD4+ observed ^[12]				Y							Y			
CD8+ observed ^[12]				Y							Y			
CD4+/CD8+ ratio observed ^[12]				Y										
HIV-1 Conditions and Disease Progression														
HIV Conditions including/excluding Recurrences as recorded in eCRF				Y			Y							
HIV Disease Progressions ^[13]				Y										

NOTES:

- T = Table, F = Figures, L = Listings, Y = Yes display generated
 - Stats Analysis = Represents TFL related to any formal statistical analyses (i.e. modelling) conducted.
 - Summary = Represents TF related to any summaries (i.e. descriptive statistics) of data.
 - Individual = Represents FL related to any displays of individual participant’s data.
1. Line plots, with 95% confidence intervals (CIs), for the proportion of participants with HIV-1 RNA ≥50 c/mL by treatment group at each visit. The 95% CIs will be calculated using Exact (Clopper-Pearson) confidence interval if the proportion is 0%; otherwise, they are derived using the normal approximation.
 2. Plot of the unadjusted treatment difference and its 95% confidence intervals (Snapshot algorithm) overall and by subgroup at Week 48/Week 96.
 3. Line plots, with 95% confidence intervals, for the proportion of participants with HIV-1 RNA <50 c/mL by treatment group at each visit. The 95% CIs will be calculated using Exact (Clopper-Pearson) confidence interval if the proportion is 100%; otherwise, they are derived using the normal approximation.
 4. Study outcomes (i.e., HIV-1 RNA <200 c/mL, HIV-1 RNA ≥200 c/mL, or reason for no data in the window) based on the snapshot algorithm at Week 48 will also be produced.
 5. Line plots, with 95% confidence intervals, for the proportion of participants with HIV-1 RNA <200 c/mL and ≥200 c/mL by treatment group at each visit. The 95% CIs will be calculated using Exact (Clopper-Pearson) confidence interval if the proportion is 0% or 100%; otherwise, they are derived using the normal approximation.
 6. Delay in IP injection (days) is defined in Section 15.6.3.
 7. Using log10 transformed values.
 8. Individual plasma HIV-1 RNA only for participants who are in the category of ‘viral load ≥50 c/mL’ at Week 48 per Snapshot algorithm or who are CVF participants. The figures will display all HIV-1 RNA values collected.
 9. For CVF participants, participants with viral load ≥ 50 c/mL during the Maintenance Phase, and participants with viral load ≥ 50 c/mL during the Maintenance oral lead-in period.
 10. See Section 15.6.3 for definition of “Target Detected” and “Target Not Detected”, and for the specification of corresponding summary table.
 11. “Target Detected” and “Target Not Detected” are included in the listing for plasma HIV-1 RNA by visit.
 12. Using available data without imputation for missing values.
 13. See Section 15.6.3 for HIV disease progressions.

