2.3. Study Design

Overview of Study Design and Key Features	

The diagram illustrates the study design timeline. It is divided into three phases: Screening Phase, Maintenance Phase, and Extension Phase. The Screening Phase starts at Day 1 and includes randomization (1:1) for two arms: the ATLAS Q4W Arm and the ATLAS SOC Arm + additional SOC Patients. The Maintenance Phase (from Day 1 to Week 100) involves randomization (1:1) into Q4W CAB LA + RPV LA and Q8W CAB LA + RPV LA regimens. The Extension Phase (starting at Week 100) involves CAB LA + RPV LA Q4W or Q8W. Key events include the 1° Endpoint at Week 48 and the 2° Endpoint at Week 100.
	

N=1020, randomized 1:1 to each arm and stratified by prior CAB+RPV Exposure
 
# SOC Patients not transitioning from the ATLAS study must be on uninterrupted current regimen (either the initial or second cART regimen) for at least 6 months prior to Screening. Documented evidence of at least two plasma HIV-1 RNA measurements <50 c/mL in the 12 months prior to Screening: one within the 6 to 12 month window, and one within 6 months prior to Screening. No history of virologic failure. No evidence of viral resistance based on the presence of any resistance-associated major INI, or NNRTI mutation (except K103N) from prior genotype assay results. No current or prior history of etravirine use.
 
†Optional Extension Phase to continue randomized CAB LA + RPV LA Q4W or Q8W at Wk 100
 
‡Participants who withdraw from IM arm must go into 52 week long term follow up phase if randomized regimen is not yet locally approved and commercially available.
	

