15.14.5.3. Efficacy Figures

Note: For subgroup analyses, include rederived randomization strata (i.e. prior exposure to CAB+RPV: 0, 1-24, >24 weeks), all demographic and baseline characteristic subgroups as mentioned in EMA Subgroup Category 2 in Section 5.4.2, unless otherwise specified. Not all subjects on Q8W arm are planned to have viral load data collected at Week 4 (Week 4A or 4B), so leave Week 4 data blank for Q8W arm in by-visit snapshot analysis.

Efficacy Figures							
No. in W48	No. in W96	No. in EOS	Population	IDSL / Example Shell	Title	Programming Notes	Deliverable
Primary Efficacy Analyses							
2.1	2.1	NA	Intent-to-Treat Exposed	201585/primary_02/F2.1	Proportion (95% CI) of Subjects with HIV-1 RNA ≥ 50 c/mL by Visit (Maintenance Phase) – Snapshot Analysis		HL, W48, W96
2.2	2.2	NA	Intent-to-Treat Exposed	201584/primary_01/F2.2	Unadjusted Treatment Difference in Proportion (95% CI) of Subjects with HIV-1 RNA ≥ 50 c/mL at Week 48 by Subgroup – Snapshot Analysis	Non-inferiority margin is 4%. Adjust the footnotes, reference line and labels as appropriate. For WK96, replace 'Week 48' with 'Week 96' in title.	W48, W96
Secondary and Exploratory Efficacy Analyses							
2.3	2.3	NA	Intent-to-Treat Exposed	201585/primary_02/F2.3	Proportion (95% CI) of Subjects with HIV-1 RNA < 50 c/mL by Visit (Maintenance Phase) – Snapshot Analysis		HL, W48, W96
2.4	2.4	NA	Intent-to-Treat Exposed	201584/primary_01/F2.4	Unadjusted Treatment Difference in Proportion (95% CI) of Subjects with HIV-1 RNA < 50 c/mL at Week 48 by Subgroup – Snapshot Analysis	Adjust the footnotes, reference line and labels as appropriate. For WK96, replace 'Week 48' with 'Week 96' in title.	W48, W96

Efficacy Figures							
No. in W48	No. in W96	No. in EOS	Population	IDSL / Example Shell	Title	Programming Notes	Deliverable
2.5	2.5	NA	Intent-to-Treat Exposed	201585/primary_02/F2.10	Proportion (95% CI) of Subjects with HIV-1 RNA ≥ 200 c/mL by Visit (Maintenance Phase) – Snapshot Analysis		W48, W96
2.6	2.6	NA	Intent-to-Treat Exposed	201585/primary_02/F2.5	Proportion (95% CI) of Subjects with HIV-1 RNA < 200 c/mL by Visit (Maintenance Phase) – Snapshot Analysis		W48, W96
2.7	2.7	2.1	Intent-to-Treat Exposed	207966/idmc_03/F2.1	Individual Plasma HIV-1 RNA (log ₁₀ c/mL) Profiles by Visit – for CVF subjects		HL, W48, W96, EOS

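### By-visit 95% error bars for HIV-1 RNA ≥50 and ≥200 c/mL use the normal approximation as soon as one event occurs, so upper limits are too low for rare failures (descriptive figures only)

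*SAP*

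**What the plan says.** SAP section 7.3, Table 3 plans by-visit line plots of Snapshot proportions. Three notes set the interval for each arm at each visit.

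- **Note 1 (≥50 c/mL):** "The 95% CIs will be calculated using Exact (Clopper-Pearson) confidence interval if the proportion is 0%; otherwise, they are derived using the normal approximation".
- **Note 3 (<50 c/mL), the mirror rule:** exact "confidence interval if the proportion is 100%; otherwise, they are derived using the normal approximation".
- **Note 5 (<200 and ≥200 c/mL):** exact "if the proportion is 0% or 100%; otherwise, they are derived using the normal approximation".

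No minimum event count and no truncation at 0% or 100% is stated. In section 15.14.5.3 the ≥50 c/mL plot is Figure 2.1, "Proportion (95% CI) of Subjects with HIV-1 RNA ≥ 50 c/mL by Visit". It stands under the primary efficacy heading and is delivered with the headline, Week 48 and Week 96 packages. The ≥200 c/mL plot is Figure 2.5, delivered at Week 48 and Week 96.

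**The concern.** Choosing an exact interval at 0% concedes that the normal approximation fails at the boundary. The rule treats that failure as ending at the first event, but with few events the binomial distribution is still strongly skewed. A symmetric (Wald) interval then reaches too far down and not far enough up. Three consequences follow:

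- Some lower limits are impossible values.
- The upper limit drops when the first failure is seen.
- Upper limits are too low, so the plot understates how high a failure rate is compatible with the data.

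At stake is how Figures 2.1 and 2.5 are read, one of which goes out with the headline results.

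**Working it through.** **Inputs**

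- Arm size: section 2.3 gives "N=1020, randomized 1:1 to each arm and stratified by prior CAB+RPV Exposure", so about 1020 / 2 = 510 per arm. Snapshot keeps every ITT-E participant in the denominator, so 510 is used at each visit.
- Confidence level: two-sided 95%, z = 1.96.
- Event counts (0 to 15) and true rates (0.5% to 4%): assumed, because the SAP states no expected failure rate. For the same reason there is no figure of the plan's own to reproduce.

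**Formulas**

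- Wald: p ± 1.96 × √(p(1 − p)/n), with p = x/n.
- Clopper-Pearson: the 2.5% quantile of Beta(x, n − x + 1) and the 97.5% quantile of Beta(x + 1, n − x). At x = 0 the upper limit is 1 − 0.025^(1/n).

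**Zero against one event**

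- 0 events (exact): 1 − 0.025^(1/510) = 0.72%.
- 1 event (Wald): p = 1/510 = 0.196%, standard error √(0.00196 × 0.99804 / 510) = 0.196%, so 0.196% ± 0.384% = −0.19% to 0.58%.

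**Limits at n = 510**

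| Events | Rule as written | Clopper-Pearson | Shortfall of upper limit (points) |
|---|---|---|---|
| 0 | 0% to 0.72% | same | none |
| 1 | −0.19% to 0.58% | 0.005% to 1.09% | 0.51 |
| 2 | −0.15% to 0.94% | 0.05% to 1.41% | 0.47 |
| 3 | −0.08% to 1.25% | 0.12% to 1.71% | 0.46 |
| 4 | 0.02% to 1.55% | 0.21% to 2.00% | 0.45 |
| 5 | 0.13% to 1.84% | 0.32% to 2.27% | 0.44 |
| 10 | 0.76% to 3.16% | 0.94% to 3.58% | 0.41 |
| 15 | 1.48% to 4.41% | 1.66% to 4.81% | 0.40 |

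The Wald lower limit is negative when x < z²(1 − p), that is, when x is below about 3.84. This is why it happens at 1, 2 and 3 events and never from 4 upward. Wilson upper limits at 1, 5 and 10 events are 1.10%, 2.27% and 3.57%, almost the same as the exact ones.

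**Coverage of the rule**, summed over the binomial distribution at n = 510:

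| True rate | Coverage | Interval wholly below the truth (nominal 2.5%) | Clopper-Pearson coverage |
|---|---|---|---|
| 0.5% | 99.9% | 0.0% | 98.5% |
| 0.75% | 89.0% | 10.4% | 96.2% |
| 1% | 87.9% | 11.5% | 97.9% |
| 1.5% | 94.3% | 5.2% | 95.9% |
| 2% | 93.4% | 5.8% | 95.9% |
| 3% | 92.9% | 5.8% | 96.4% |
| 4% | 93.2% | 5.3% | 95.9% |

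The 1% row can be checked by hand. The upper limits at 0, 1 and 2 events (0.72%, 0.58%, 0.94%) all lie below 1%, and the chance of 0, 1 or 2 events is 0.59% + 3.06% + 7.87% = 11.5%.

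Coverage oscillates because the data are discrete. It is 94.1% at 0.9%, 85.9% at 0.95% (13.7% of intervals wholly below the truth) and 94.8% at 1.25%.

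**The case against.** The strongest objection is that nothing is decided by these intervals. Table 3 sits under exploratory efficacy and marks the plots as summaries, not as formal statistical analysis. The primary rule in section 7.1.5.1 compares the upper confidence limit of a stratified difference, which has its own variance estimator, with the 4% margin. The key secondary test in section 7.2.5.1 uses the same method. Subgroup differences use an unconditional exact interval. A reader might infer from the heading over Figure 2.1 that the primary result is affected. The SAP does not support that: the primary result is Table 2.1, which does not use this rule. This part of the objection stands and sets the weight of the point.

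Two other stronger readings also fail. Negative lower limits are not general. They need 1 to 3 events in an arm at a visit, which has a 24% chance at a true rate of 1% and under 1% at 2%. Nor is coverage near 88% typical. It belongs to a trough around 0.75% to 1%, and at 0.5% the rule over-covers. The 1% rate is an assumption, not a figure from the plan.

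Finally, the <50 and <200 c/mL plots are usually little affected. Participants without virologic data do not count as suppressed (section 15.7.2.2), which can hold the proportion well below 100%. At an illustrative 470 of 510, the rule gives 89.8% to 94.5% against an exact 89.5% to 94.3%.

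The objection does not rescue the rule for rare failures. The upper limit is too low at every non-zero count examined, and nothing elsewhere in the SAP corrects it.

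**Conclusion.** The interval rule in notes 1 and 5 is wrong as written for the ≥50 and ≥200 c/mL by-visit plots. The practical effect is an upper limit about 0.4 to 0.5 points too low at 1 to 15 events. At the tabulated true rates from 0.75% to 4%, intervals lie wholly below the truth roughly 5% to 12% of the time instead of 2.5%. From 1.5% upward the loss of coverage is only about 1 to 2 points. These sizes assume 510 per arm and the event counts and rates listed.

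Severity is minor: two descriptive figures carry misleading error bars, one of them in the headline package, and no test, margin or decision changes.

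**What to change.** In Table 3 notes 1 and 5, use Clopper-Pearson at every count for the ≥50 and ≥200 c/mL plots and delete the normal-approximation clause. Wilson would serve equally well. Make the same change for <50 c/mL (note 3) and <200 c/mL (note 5) for consistency, although the effect there is usually immaterial.

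The exact method is already named in all three notes, so this removes a branch from the code and adds no new method. It needs no new data and does not touch the type I error or the decision rule. The cost is slightly wider, mildly conservative bars: Clopper-Pearson coverage was 95.9% to 98.5% at the rates tabulated.
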